### 6.1.3. Intercurrent Events and Handling Strategies

The following table listed outs some potential intercurrent events that may impact the estimation of the primary estimand of the study. For each type intercurrent event, we proposed handling strategies:

Events	Potential Consequences	Handling Strategy
Early discontinuation and/or missing because of:  1. Lack of efficacy; physician decision; or required prohibited medication;  2. Adverse events or death;  3. Noncompliance to study drug;  4. Other reasons for treatment discontinuations	
 
• Confounded treatment effect
 
	Hypothetical Policy 
 
• Sensitivity Analysis:               
 
– MAR
 
– MNAR
 
 
 

Concomitant Medications	
 
• More difficult to pinpoint           
 
○ Administered as needed for both active treatment and placebo
 
○ May lead to various impacts on participants' treatment/safety/efficacy
 
 
 
	Randomization/Treatment Policy
Other Intrinsic/extrinsic factors 
 
• Stratification factors
 
• Age
 
• Sex
 
• Race/Ethnicity
 
	
 
• Differentiated treatment effects
 
	Principal Stratum Policy 
 
• Stratified analyses
 
• Subgroup analyses
 
• Covariate adjusted analyses
 

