#### Primary Estimand for Primary Efficacy Endpoint

The primary estimand efficacy endpoint is to evaluate the superior efficacy of volixibat versus placebo for the reduction of elevated sBA concentrations in participants with ICP. The primary comparison of interest is the mean change in sBA concentration comparing baseline with Week 3. The primary comparison will be made regardless of adherence to randomized treatment, treatment modification, or treatment termination and irrespective of any changes in or initiations of allowed concomitant therapies, while assuming that prohibited medications are not available.

The corresponding primary estimand is described by the following 5 attributes:

- Treatments: The randomized treatment administered BID until delivery (with at least 1 dose), regardless of adherence to randomized treatment, treatment modification, or treatment termination
- Population: Participants with ICP who have an sBA concentration  $\geq 20$   $\mu\text{mol/L}$  and an average daily score of  $\geq 4$  on the Adult ItchRO during the screening period. Further population criteria details are provided in [Sections 5.1](#) and [5.2](#).
- Endpoint: Change in the sBA concentration comparing baseline with Week 3
- Population-level summary: Difference in the mean change in the sBA concentration
- Intercurrent events:
  - Change in or administration of any allowed concomitant medication will be handled using a treatment policy strategy.
  - Administration of any prohibited concomitant medication will be handled using a hypothetical strategy assuming that the prohibited medications are not available and hence were not taken, so as to assess the treatment effect for the randomized treatment groups on top of allowed concomitant medication.
  - Discontinuation of randomized treatment due to all of the following reasons will be handled using a treatment policy strategy:
    - Lack of efficacy
    - Safety concerns
    - Lack of compliance to study treatment
  - Delivery prior to 3 weeks of treatment will be handled using a hypothetical strategy, assuming that delivery has not occurred. Few early deliveries are expected prior to Week 3. Participants with sBA  $< 100$  are not likely to give birth prior to 39 weeks, which is at least 3 weeks after the first dose date based on

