eligibility criteria (see [Section 8.1.12](#)). Participants with sBA >100 at 34 weeks would have been randomized at least a week earlier (i.e., 33 weeks) because a planned birth within 7 days of randomization is exclusionary. It is anticipated that these participants would still be able to remain on treatment for 3 weeks before giving birth.

- Perinatal death prior to 3 weeks of treatment will be handled using a hypothetical strategy, assuming perinatal death has not occurred. Very few, if any, perinatal deaths are expected prior to Week 3.
- Discontinuation of randomized treatment due to other reasons (including loss to follow-up) will be handled using a hypothetical strategy, assuming that randomized treatment had not been discontinued.
- Liver transplant or death: Neither of these are expected in the study. In the unlikely event of this happening, they will be treated using a composite strategy, assuming worse case for all subsequent assessments.

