### **Part 1: Proof of Concept, Dose Ranging, Pharmacokinetics, and Interim Analysis**

After a screening period of up to 10 days, eligible participants will be identified for one of two cohorts, defined as follows:

- Primary cohort: Participants with ICP with a screening sBA level  $\geq 20$   $\mu\text{mol/L}$  will be randomized with stratification (based on gestational age [ $<32$  weeks or  $\geq 32$  weeks] at randomization, presence/absence of gestational diabetes, and highest sBA before randomization [ $<40$   $\mu\text{mol/L}$ ,  $\geq 40$   $\mu\text{mol/L}$  to  $<100$   $\mu\text{mol/L}$ , or  $\geq 100$   $\mu\text{mol/L}$ ]) in a 3-arm (1:1:1), double-blind fashion to receive volixibat 20 mg BID, volixibat 80 mg BID, or placebo.
- Supplemental cohort: Up to 30 participants with ICP with screening sBA level from  $\geq 15$  to  $<20$   $\mu\text{mol/L}$  will be randomized (based on gestational age at randomization and presence/absence of gestational diabetes) in a 2-arm (1:1), open-label fashion to receive volixibat 20 mg BID or volixibat 80 mg BID.

Study treatment dosing will begin on Day 1 and continue until end of the study treatment period, defined as the day of delivery. Study visits to assess safety, plasma concentrations of volixibat, pharmacodynamics, and efficacy will be conducted weekly from baseline until

delivery. Because alternative measures may be implemented when necessary for public health or other emergency situations, and when sufficient to help ensure the safety of study participants, some visits may be conducted as a home health or remote visit at the discretion of the investigator upon approval by the medical monitor or designee and in accordance with local and regional regulations (see Protocol Appendix 10). Participants will also enter ItchRO assessments into an electronic diary (eDiary) once daily. Use of limited rescue therapies for ICP will be permitted for participants who meet protocol-specified criteria.

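### SAP 6.1.3 (and 3.8.3 for early delivery) does not implement the intercurrent-event strategies of the current protocol's primary estimand

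*SAP*

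**What the plan says.** **Protocol 10.4.1.1** (primary estimand for change in total sBA to Week 3) sets a strategy for each kind of event:

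- Stopping drug for lack of efficacy, safety concerns or noncompliance: "Discontinuation of randomized treatment due to all of the following reasons will be handled using a treatment policy strategy".
- Stopping for anything else: "Discontinuation of randomized treatment due to other reasons (including loss to follow-up) will be handled using a hypothetical strategy".
- Allowed concomitant medication is treatment policy. For the rest, "Administration of any prohibited concomitant medication will be handled using a hypothetical strategy".
- Early delivery: "Delivery prior to 3 weeks of treatment will be handled using a hypothetical strategy, assuming that delivery has not occurred". Perinatal death before Week 3 is handled the same way.
- For liver transplant or death, "they will be treated using a composite strategy, assuming worse case for all subsequent assessments".

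**SAP 6.1.3** offers a table of "some potential intercurrent events that may impact the estimation of the primary estimand". Its first row is headed "Early discontinuation and/or missing because of" and has four items: lack of efficacy, physician decision or required prohibited medication; adverse events or death; noncompliance; and other reasons for stopping. The whole row has one strategy, hypothetical, with MAR and MNAR sensitivity analyses. A second row, for concomitant medications without subdivision, is treatment policy. Delivery before Week 3, perinatal death and liver transplant have no row.

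**SAP 3.8.3** assigns the sBA from a delivery before Week 3 to the window after the last visit. Its example maps a Day 18 delivery value to Week 3 and gives the aim as limiting missing primary data.

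**SAP 1** says that the SAP is based on protocol Version 1 of 14 October 2020.

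**The concern.** The strategies for intercurrent events define what the primary test estimates. Part 2 has one success criterion, the Week 3 treatment contrast at two-sided 0.05. For that test the two documents name different estimands. Under treatment policy, the effect includes what happens to sBA after a participant stops drug for an efficacy, safety or compliance reason. Under a hypothetical strategy, it is the effect had she not stopped.

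The SAP row also merges two separate matters: an event that changes the meaning of later values, and values that do not exist. A programmer given this row cannot tell whether an sBA measured after stopping drug should be used. The protocol's estimand needs that value for three reasons and sets it aside for others. If the choice is made after unblinding, the confirmatory p-value loses its prespecified meaning.

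**Working it through.** No figure in the plan is in dispute, so the check is a comparison of text. The protocol has seven intercurrent-event bullets; two are split below because the SAP treats their parts differently.

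| Event | Protocol 10.4.1.1 | SAP 6.1.3 | Result |
|---|---|---|---|
| Stop: lack of efficacy | Treatment policy | Hypothetical | Conflict |
| Stop: safety concerns (SAP: adverse events) | Treatment policy | Hypothetical | Conflict |
| Stop: noncompliance | Treatment policy | Hypothetical | Conflict |
| Death of participant | Worst-case composite | Hypothetical | Conflict |
| Prohibited medication | Hypothetical | Hypothetical if it led to stopping; otherwise only the undivided treatment-policy row | Partial |
| Allowed medication | Treatment policy | Treatment policy | Agree |
| Stop: other reasons | Hypothetical | Hypothetical | Agree |
| Delivery before Week 3 | Hypothetical | No row | Silent; see 3.8.3 |
| Perinatal death before Week 3 | Hypothetical | No row | Silent |
| Liver transplant | Worst-case composite | No row | Silent |

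**Are the off-drug values collected?** Yes. Both schedules of activities keep weekly visits going after drug is stopped, and sBA is drawn at those visits.

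**Does the SAP say whether they are used?** No sentence does. Several places bear on it indirectly:

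- SAP 6.1.2 models weekly changes through Week 3 in the double-blind treatment period and gives no rule for removing off-drug values.
- SAP 1.2, in its description of Part 1, says: "Study treatment dosing will begin on Day 1 and continue until end of the study treatment period, defined as the day of delivery". This suggests that the period does not end at the last dose.
- SAP 6.1.7 counts anyone with baseline and Week 3 sBA as non-missing, but it is a sensitivity imputation.
- SAP 6.1.5 drops post-rescue data only in a separate repeat analysis.

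**Does either reading give the protocol's estimand?**

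- *Exclude all values after stopping, as the label implies.* This removes data that treatment policy needs for lack of efficacy, safety and noncompliance, and death does not get its worst-case value. Values after prohibited medication that did not lead to stopping remain, under the undivided medication row.
- *Keep all observed values.* This serves the three treatment-policy reasons. It also keeps values after prohibited medication and after stopping for other reasons, both hypothetical in the protocol.

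Neither reading works.

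**Delivery before Week 3.** SAP Table 2 sets the window for Week K as K×7−2 to K×7+4.

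- Week 2: 2×7−2 = 12 to 2×7+4 = 18.
- Week 3: 3×7−2 = 19 to 3×7+4 = 25, nominal day 3×7+1 = 22.

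The Day 18 value in the SAP's example therefore lies in the Week 2 window, 22−18 = 4 days before nominal Week 3. Both schedules let the delivery sample be taken without regard to meals, while other visits aim for 30–90 minutes postprandially. Using that value as the Week 3 result is not the same as assuming that delivery had not occurred.

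**The case against.** The strongest reply is that the SAP is out of date rather than wrong. It follows protocol Version 1 and describes another design: a double-blind three-arm Part 1, a supplemental cohort and baseline no later than 35 weeks 0 days. The protocol already requires a final SAP before unblinding. This explains the mismatch but does not remove it; the items in the table are what the update has to contain.

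A reader might go further and infer an undocumented deviation, since SAP 1 promises to record deviations, Section 6 records none and the revision table is blank. The documents do not support that. Version 1 is not among them, so SAP 6.1.3 may have matched it.

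Second, the row can be read as a missing-data rule with a poor label, in which case off-drug sBA is kept and the three discontinuation reasons are analysed as the protocol intends. That is plausible. It is tempting to conclude that the label contradicts the SAP's own data rules, but no sentence governs off-drug values, and the clearest hint is a sensitivity rule. Even on this reading, prohibited medication and other-reason discontinuation are not handled as the protocol requires.

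Third, the protocol expects few early deliveries, very few if any perinatal deaths, and no transplants or deaths. This stands and lowers the weight of those items. Early delivery cannot be dismissed altogether: Part 2 enrols up to 36 weeks 0 days and has a stratum at or above 100 µmol/L, for which the guidance cited in Protocol 8.1.12 discusses planned birth at 35–36 weeks.

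Fourth, the SAP table claims only partial coverage, so its absent rows are omissions rather than conflicts. That is accepted. ItchRO is similar: Protocol 10.4.1.3 defines its estimand, and SAP 6.2 is silent without contradicting it.

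**Conclusion.** The mismatch with the current protocol is established by the text. The SAP applies a hypothetical strategy to three discontinuation reasons that the protocol assigns to treatment policy, and to death, which the protocol assigns to a worst-case composite. Its undivided medication row does not carry the protocol's hypothetical strategy for prohibited medication. It does not say which off-drug values enter the primary model, and neither reading yields the protocol's estimand. The delivery-day mapping is a separate inconsistency.

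No size is claimed. A reader might infer a biased estimate or lost power, but that would need a discontinuation rate and the effect retained off drug, and neither document gives them. Most of the practical weight lies with the three discontinuation reasons and prohibited medication. The conclusion assumes that the SAP's adverse events and the protocol's safety concerns are the same category, and that death in both lists means death of the participant. It should be settled before unblinding because it fixes what the confirmatory test estimates.

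**What to change.** Before unblinding, revise the SAP as follows:

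1. Rewrite 6.1.3 reason by reason to match Protocol 10.4.1.1, say which class physician decision belongs to, and move missing-data handling elsewhere.
2. State that sBA observed through Week 3 after stopping drug for lack of efficacy, safety or noncompliance is included in the primary MMRM.
3. State that values after prohibited medication, or after stopping for other reasons, are handled hypothetically, and how. Limit the treatment-policy medication row to allowed medication.
4. Move death to the composite strategy, add liver transplant, and specify the worst-case value.
5. Add rows for delivery and perinatal death before Week 3, and reconcile 3.8.3 with the protocol. One option is to run the analysis with and without the mapped delivery-day value and name which is primary.
6. Carry the same strategies to ItchRO, as Protocol 10.4.1.3 requires.

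The cost is SAP text plus flags for the reason for stopping drug and the start date of prohibited medication. No new assessments are needed, since weekly sBA after stopping is already scheduled. If the delivery-day value is left out of the primary analysis, some more Week 3 values will be missing, which is what 3.8.3 was written to avoid.

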#### 6.1.4. Rationale for Primary Analysis Method

The MMRM method has been demonstrated extensively as an appropriate choice for the primary analysis in longitudinal confirmatory clinical trials with continuous endpoints ([Mallinckrodt et al. 2008](#)). This analysis method, which is from a broader class of direct-likelihood analyses methods, makes use of fully and partially observed data sequences from individual participants by estimating the covariance between data from different time points ([Molenberghs and Kenward 2007](#)). Further, it is often useful to implement MMRM using an unstructured approach to modeling both the treatment-by-time means and the (co)variances, leading to what is essentially a multivariate normal model wherein treatment group means at the primary time point are adjusted to reflect both the actual observed data and the projected outcomes from the participants with missing data ([Cnaan et al. 1997](#); [Molenberghs et al. 2004](#); [Molenberghs and Kenward 2007](#)).

Despite careful planning and study conduct, the occurrence of missing data cannot be completely eliminated. As a direct likelihood method, the MMRM method is a preferred approach for handling missing data in such designs. MMRM is a full multivariate model in nature that avoids potential bias as a predetermined model and operates in a more general missing at random (MAR) framework ([Mallinckrodt et al. 2001](#)). Data are considered MAR if, conditional upon the independent variables in the analytic model, the missingness depends on the observed outcomes of the variable being analyzed but does not depend on the unobserved outcomes of the variable being analyzed. This assumption implies that the behavior of the post dropout observations can be predicted from the observed variables, and therefore that treatment effect can be estimated without bias using the observed data ([European Medicines Agency 2010](#)). For studies of missing data in a controlled clinical trial setting, MAR is usually considered as a plausible underlying missing mechanism ([Molenberghs and Kenward 2007](#); [Siddiqui et al. 2009](#); [Mallinckrodt et al. 2008](#), [Mallinckrodt et al. 2013](#)). The assumption of MAR is often reasonable because, particularly in longitudinal studies wherein the evolution of treatment effects is assessed by design over time, the observed data and the models used to analyze them can explain much of the missingness ([Little and Rubin 1987](#); [Verbeke and Molenberghs 2000](#)). This point may be especially relevant in well-controlled studies, in which extensive efforts are made to observe

all outcomes and factors that influence them while participants are following protocol-defined procedures. Thus, longitudinal clinical trials by their very design aim to reduce the amount of missing not at random (MNAR) data (missingness explained by unobserved responses), thereby increasing the plausibility of MAR ([Mallinckrodt et al. 2008](#)).

#### **6.1.5. Sensitivity Analysis of the Primary Efficacy Endpoint**

Sensitivity and supportive analysis will be performed on the primary efficacy endpoint to quantify the possible impact of missing data, intercurrent events and to demonstrate the robustness of the conclusions. See below for details about missing data handling, placebo-based imputation, and a tipping-point analysis.

Furthermore, the primary analysis will be repeated using a hypothetical (de jure) estimand where data collected after rescue medication is initiated will be omitted. This can be viewed as addressing a per protocol estimand, or more simply the applicable estimand if all participants completed the first 3 weeks of follow-up without any rescue or without any missing data.

#### **6.1.6. Missing Data**

Although the assumption of MAR, as used for the primary efficacy analysis method, is often reasonable in clinical studies, the possibility of MNAR data cannot be ruled out. Therefore, examining the robustness of the primary analysis results under MNAR is desired. Both a MNAR- and MAR-based analyses will be the basis upon which sensitivity of missing data is assessed.

Sensitivity analyses to deal with missing data and intercurrent events will be based on multiple imputation methods where missing values are imputed individually under different assumptions. Multiple imputation is a simulation-based approach where missing values are replaced using an appropriate stochastic model given the observed data and covariates, creating multiple completed data sets. These completed datasets are then analyzed using standard analysis methods (i.e., MMRM), and the different parameter estimates across the datasets are then combined to produce a unique point estimate and standard error taking into account the uncertainty of the imputation process. The following 2 sensitivity analysis models, one based on the standard MAR approach and the other based on the MNAR approach, will be used to examine robustness of the primary analysis results under the impact of missing data and intercurrent events.

#### **6.1.7. Complete Multiple Imputation Differentiating Intereurrent Events**

For participants with complete data up to a particular visit, a distribution will be assumed for the assessments includes the outcome at that visit based on predefined missing categories and types of intercurrent events. The missing data then will be imputed based on specified algorithm which draws samples based on the prespecified distribution and algorithm. This process will be repeated a given number of times, resulting in the same number of complete analysis data sets. The MMRM analyses then will be performed separately for each of the completed analysis data sets, and the results will be combined into one multiple imputation inference ([Little and Yau 1996](#); [Schafer 1997](#)). Example SAS code is provided in [Appendix 3](#).

### **Imputation distribution:**

The imputation distribution for the missing change from baseline in sBA at visit  $t$  will be assumed to follow a normal distribution. All randomized participants will be classified in one of the three categories based on the following rules: non-missing category, missing category 1, or missing category 2,

Non-missing category: Participants who have completed sBA assessment at baseline and Week 3 and have the change from baseline Week 3.

Missing category 1: Participants who discontinued treatment because of adverse events, lack of efficacy, noncompliance with study drug, death, physician decision, or required prohibited medication. These participants have missing change from baseline in sBA at visits including Week 3.

Missing category 2: Participants who discontinued treatment because of all other reasons other than the ones listed in category 1 and have missing the change from baseline in sBA at visits including Week 3, or participants who have completed 3 weeks treatment duration but are missing the change from baseline in sBA at visits including Week 3.

### **Imputation algorithm:**

We use the following algorithm that relates the mean of the missing change from baseline in sBA at visit  $t$  to the missing categories defined above. The algorithm will be implemented independently within each treatment group:

- **Missing category 1**: randomly draw a sample from the normal distribution  $N(\mu_{25}, \sigma^2)$ , where  $\mu_{25}$  is the 25th percentile of the non-missing change from baseline in sBA at visit  $t$  and  $\sigma^2$  is the sample variance estimated using the non-missing change from baseline at visit  $t$ .
- **Missing category 2**: randomly draw a sample from the normal distribution  $N(\mu, \sigma^2)$ , where  $\mu$  is the mean of the non-missing change from baseline in sBA at visit  $t$  and  $\sigma^2$  is the sample variance estimated using the non-missing change from baseline at visit  $t$ .

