## 10.1. Sample Size Determination

Part 1 of the study is designed for estimation without formal statistical testing; hence, there are no formal power considerations. For example, with 20 participants per group and assuming a standard deviation of 25 for each group, a 95% CI for the mean for each volixibat arm would have a half width of 11.

For the power calculations for Part 2, it is assumed that only a single dose will be selected at the end of Part 1, and a 2-sided alpha 0.05 will be used to test whether there is a difference between the 2 groups. Thus, for Part 2, a sample size of 100 participants per arm has 80% power to detect mean difference of 10 with standard deviation of 25. Power was calculated using SAS, version 9.4.

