### **Standard MAR Imputation**

The MAR imputation model will impute missing values using a regression-based MI model (Little and Yau 1996). For participants with complete data up to a particular visit, a multiple regression model will be fit that includes the outcome at that visit as the dependent variable and observed data (e.g., outcomes at previous visits, treatment, and baseline) as independent variables. Separate models will be similarly constructed for each visit. Using these regression

models, a missing value for a participant at a particular visit will be imputed as a draw from the predictive distribution given the outcomes at previous visits (some possibly imputed), treatment group, etc. This process will be repeated a given number of times (as specified in the SAP), resulting in the same number of complete analysis datasets. The MMRM analyses will be performed separately for each of the completed analysis datasets, and the results will be combined into 1 MI inference (Little and Yau 1996; Schafer 1997). This strategy is appropriate for datasets that have a monotone missing data pattern. If the dataset does not precisely have this pattern, a monotone data augmentation method, as described in the SAP, will be used to impute the small amount of missing data that is required to make the missing data pattern monotone before applying the MI algorithm described above.

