### **1.3. Sample Size Determination**

For the interim analysis at the conclusion of Part 1, 60 participants will have been randomized 1:1:1. Part 1 of the study is designed for estimation without formal statistical testing; hence, there are no formal power considerations. With 20 participants per arm and assuming a (pooled) standard deviation of 25, a 95% confidence interval (CI) for the difference between each volixibat arm and placebo would have a half width of 16.

For the power calculations for Part 2, it is assumed that only a single dose will be selected at the end of Part 1, and a 2-sided alpha 0.05 will be used to test whether there is a difference between the two groups. Thus, for Part 2, a sample size of 100 participants per arm has 80% power to detect an effect size of 10 with standard deviation of 25. Power was calculated using SAS, version 9.4.

Up to 30 additional participants will be enrolled in an open-label supplemental cohort consisting of participants with ICP with screening sBA from  $\geq 15$  to  $< 20$   $\mu\text{mol/L}$  in a 1:1 manner to the two doses of volixibat.

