### 6.1.8. Tipping Point Analysis

An additional sensitivity analysis using the tipping-point approach will be conducted to assess the robustness of the primary analysis approach. If it is plausible that, for the active treatment group, the distribution of missing primary endpoint responses has a smaller expected reduction than that of the corresponding distribution of the observed primary endpoint responses, the conclusion under the MAR assumption should be examined. It is desired to impose a fixed and definite set of quantities to encapsulate the change in efficacy associated with withdrawal (missing) for the active treatment group, and independently for the placebo group. The tipping point multiple imputation analysis as described by Ratitch et al. (2013) will be applied. Tipping point analysis is a means of exploring the influence of missingness on the overall conclusion from statistical inference by positing a wide spectrum of specifications regarding the missingness mechanism (from less pessimistic to more pessimistic). The analysis finds a (tipping) point in this spectrum of specifications, at which conclusions change from being favorable to the experimental treatment to being neutral. The analysis will be based on the following procedure:

1. The missing data are filled in  $m$  ( $m = 10$ ) times to generate  $m$  complete data sets assuming that we do not differentiate missing data category (similar to assuming the algorithm for missing category 2).
2. The  $m$  complete data sets are analyzed by using standard procedures.
3. The results from the  $m$  complete data sets are combined for the inference.

4. Repeat the steps #1 to generate multiple imputed data sets, with a specified shift parameter that adjust the imputed values for observations in the relevant treatment group independently.
5. Repeat the step 2 for the imputed data sets with shift parameter applied.
6. Repeat the step 3 to obtain the p-value to see if the p-value is still  $\leq 0.05$ .
7. Repeat the steps 4-6 with more stringent shift parameter applied until the p-value  $> 0.05$ .

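### The SAP's category 2 imputation, and by its text the tipping-point base, ignore each participant's earlier sBA; this is not MAR, conflicts with the protocol and Appendix 3, and can bias the check either way

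*SAP*

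**What the plan says.** SAP 6.1.6 promises two sensitivity models for the primary endpoint, "one based on the standard MAR approach and the other based on the MNAR approach". SAP 6.1.7 then sorts participants with missing Week 3 data into two groups.

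- Category 1 holds those who stopped for adverse events, lack of efficacy, noncompliance, death, physician decision or prohibited medication. Their values are drawn around the 25th percentile of the observed changes.
- Category 2 holds all other discontinuations, and those who completed three weeks but lack the value. Their values are drawn from a normal distribution whose centre "is the mean of the non-missing change from baseline in sBA at visit" t, with the sample variance at that visit.

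On both: "The algorithm will be implemented independently within each treatment group". The step is repeated visit by visit to form K = 5 data sets.

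SAP 6.1.8 builds its starting data sets (m = 10) without separating the categories, "similar to assuming the algorithm for missing category 2".

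The protocol (Section 10.4.1.1, Standard MAR Imputation) specifies something else. A missing value "will be imputed as a draw from the predictive distribution given the outcomes at previous visits", treatment group and other observed data, from regressions fitted at each visit. The protocol also specifies placebo-based imputation as the MNAR model, and leaves the number of imputations and the seed to the SAP.

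SAP Appendix 3 contains copy-reference code and tipping-point code. Both complete the data to a monotone pattern and then use regression on baseline and earlier visits. Neither implements the 6.1.7 algorithm.

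**The concern.** SAP 6.1.4 defines MAR as missingness that may depend on observed outcomes. A draw from the arm's marginal distribution does not allow for that. A participant with a poor Week 2 value and a missing Week 3 value is imputed as if nothing were known about her, that is, as a typical observed member of her arm. If such participants are lost more often in one arm, that arm's Week 3 mean is made to look better than it is.

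The primary MMRM uses the earlier visits and so corrects for this kind of loss. The analysis meant to test the MMRM would then rest on a stronger and less plausible assumption than the MMRM itself. It could appear to confirm a result, or to undermine one, for reasons unrelated to the treatment.

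A link between sBA and missingness is plausible here. The delivery-timing guidance in protocol 8.1.12 depends on sBA, and delivery is not on the category 1 list.

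Two further weaknesses are smaller. Treating the mean and variance as known leaves parameter uncertainty out of the imputation. Drawing each visit separately breaks the within-participant correlation that the MMRM then models.

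**Working it through.** **The plan's own figure.** Inputs from SAP 1.3 and protocol 10.1: 100 per arm, difference 10, SD 25 (taken as µmol/L), two-sided alpha 0.05, 80% power. The standard error is 25 × √(2/100) = 3.54. Power = Φ(10/3.54 − 1.96) = Φ(0.87) = 80.7%, or 80.4% with the t distribution. The required n is 99 per arm. The stated 80% reproduces.

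**Inputs the documents do not give.** They state no missing rate, no visit correlation and no dropout mechanism; SAP 6.1.2 expects only minimal missing data. The values below are assumptions.

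**Analytic size.** For a marginal draw in one arm, bias = p × ρ × SD × gap. Here p is the proportion missing, ρ the correlation with Week 2, and gap the Week 2 difference between missing and observed participants in SD units. With SD 25, gap 1 and ρ from 0.5 to 0.7:

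- 5% missing: 0.05 × 0.5 × 25 = 0.6, to 0.05 × 0.7 × 25 = 0.9
- 10% missing: 1.25 to 1.75
- 20% missing: 2.5 to 3.5
- 30% missing: 3.75 to 5.25

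The bias in the treatment difference is the net of the two arms.

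**Simulation.** Settings: 1,500 trials per scenario; 100 per arm; SD 25; correlation 0.7 between visits; Weeks 1 and 2 complete; log-odds of a missing Week 3 value rising by 1.5 per SD of worse Week 2 value; K = 5; Rubin's rules; Week 3 means compared without covariates. All missing values go through the category 2 draw. The comparator is regression on Weeks 1 and 2 with parameters drawn from their posterior. The Monte Carlo error of each mean estimate is about 3.54/√1500 = 0.09.

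True difference 0 (negative favours volixibat; V/P = volixibat/placebo):

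| Missing V/P | Marginal draw: estimate | Rejects for V / for P | Regression: estimate | Rejects for V / for P |
|---|---|---|---|---|
| 20%/20% | -0.07 | 2.7% / 2.8% | -0.07 | 2.3% / 2.6% |
| 20%/5% | -2.95 | 13.3% / 0.5% | -0.09 | 2.8% / 2.5% |
| 20%/0% | -3.92 | 18.4% / 0.1% | +0.03 | 2.5% / 2.3% |
| 30%/10% | -3.60 | 16.6% / 0.2% | -0.04 | 3.1% / 2.1% |
| 5%/20% | +2.91 | 0.2% / 11.8% | +0.09 | 1.8% / 2.1% |
| 0%/20% | +3.85 | 0.2% / 17.9% | -0.15 | 2.5% / 2.2% |
| 10%/30% | +3.49 | 0.1% / 15.7% | -0.15 | 2.9% / 2.3% |

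The nominal rate in each direction is 2.5%. With a true difference of -10, the marginal draw gave -12.88 at 20%/5%, -7.29 at 5%/20% and -10.02 at 20%/20%. Regression gave -10.11, -10.12 and -10.05.

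At 20%/20% total rejection was 5.5% for the marginal draw and 4.9% for regression. The missing parameter uncertainty is therefore minor in this setting; the ignored history does the damage.

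**Number of imputations.** The draws add Monte Carlo variance of (25²/100) × (p1 + p2)/K to the combined estimate. With K = 5 the standard error is √(6.25 × 0.2/5) = 0.5 at 10% missing per arm, and √(6.25 × 0.4/5) = 0.7 at 20%. With K = 100 it is 0.11 and 0.16.

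**Text against code.** The 6.1.8 text points to category 2. Its Appendix 3 code says it imputes under MAR first, with baseline and earlier visits in the regression. The code is also an unadapted template: it carries a Week 24 label and country and sex terms, and its second step reads the output of the copy-reference program rather than its own first step. SAP 6.1.5 announces placebo-based imputation below, but it appears only as Appendix 3 code, not in the method text.

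**The case against.** Several points on the other side stand.

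- A reader might infer that the check is tilted towards volixibat. The documents do not support that. Equal loss cancels the bias, and excess placebo loss reverses it.
- A reader might infer that, under 6.1.7, participants who leave for lack of efficacy or adverse events are imputed as average completers. They are not: they fall in category 1 and are drawn around the 25th percentile. Whether that is the pessimistic tail is a separate question, not measured here. The simulated figures apply to category 2 missingness, and to 6.1.8 if its text is followed, because 6.1.8 does not separate the categories.
- A reader might take it as settled that the tipping point starts from marginal draws. The text says only that its approach is similar to category 2, and the code does otherwise. The supportable finding is a contradiction within the SAP.
- Missing data may be few. Participants who stop drug stay on weekly visits (protocol 7.1), and SAP 3.8.3 maps a delivery after the Week 2 visit to Week 3.
- Appendix 3 fixes a seed, so the noise from few imputations is not analyst discretion.
- The SAP is based on protocol Version 1 of October 2020, which may explain the departure from the current protocol.

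None of this makes the category 2 draw valid under MAR, or removes the conflict with SAP 6.1.6, the current protocol and Appendix 3.

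**Conclusion.** The point holds as a two-sided one. As written, the category 2 draw in 6.1.7 is not an MAR imputation. Following the text of 6.1.8 would carry the same fault into the tipping-point base, so its shifts would be measured from a starting point that is not MAR.

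If missingness follows earlier sBA and differs by arm, the sensitivity estimate can move by about 3 to 4 µmol/L in either direction at 20% missing in one arm and 0 to 5% in the other. That is 30 to 40% of the design difference of 10. With equal loss the shift is about 0, and at 5% missing in one arm it is below 1. These sizes rest on SD 25, a correlation of 0.7 (0.5 to 0.7 in the analytic range) and dropout driven by Week 2, none of which except the SD comes from the documents. The simulation also omits baseline adjustment.

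It would go too far to read this as a threat to the primary result. The success criterion in SAP 6.1.2 rests on the MMRM, which uses the earlier visits. What is at stake is whether the robustness analyses are prespecified without contradiction and test what they claim to test.

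**What to change.** Before unblinding:

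1. Replace the category 2 draw in 6.1.7 with the protocol's sequential regression: monotone completion, then regression on baseline, earlier visits, treatment and the model covariates, with parameters drawn from their posterior.
2. Use the same model as the unshifted base of the tipping-point analysis in 6.1.8.
3. Write the protocol's placebo-based imputation into the SAP method text as the MNAR model.
4. State one larger number of imputations (for example 100) and a seed for all of these analyses.
5. Adapt the Appendix 3 code to this trial's model, visits and data set names, so that 6.1.7, 6.1.8 and the appendix describe the same analysis.

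The cost is editing two SAP sections and one appendix, with slightly more computing. No change to the design, data collection or primary analysis is needed.
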